4.4.4 Efficacy

The efficacy endpoints are the virologically-confirmed COVID-19 illness and serologic SARS-CoV-2 infection.

Virologically-confirmed COVID-19 illness

Virologically-confirmed COVID-19 illness is defined as a positive result for SARS-CoV-2 by Nucleic Acid Amplification Test (NAAT) on a respiratory sample in association with a COVID-19-like illness, which is defined in the protocol section 8.2.2.1.

Serologic SARS-CoV-2 infection

Serologic SARS-CoV-2 infection is defined as a positive result in serum for presence of antibodies specific to non-Spike protein of SARS-CoV-2 detected by ELISA assay.

4.4.5 Other Derived Variables

4.4.5.1 Age for Demographics

The quantitative descriptive statistics (e.g., Mean, SD, Max, Min, Median, Q1 and Q3) of age in demographics summary table(s) is based on the age in year collected in eCRF.

Age group

The age in year collected in eCRF will be used for demographics summary and age sub-groups definition. The age groups of a participant used in the study are as follows:

“18 to 49 years”, “Over 50 years” and “Over 60 years”

4.4.5.2 Duration of the Study

The duration of the study is computed in days as follows:

- Maximum (latest date of Visit, latest date of termination) – minimum (date of V01) +1

4.4.5.3 Subject Duration

The duration of a subject participation in the study is computed as follows:

Maximum (Visit dates, Termination date) – V01 date + 1.

5 Statistical Methods and Determination of Sample Size

The statistical analyses will be performed under the responsibility of the Sponsor’s Biostatistics platform using SAS® Version 9.4 or later.

The results of the statistical analysis will be available in the final clinical study report (CSR).

For descriptive purposes, the following statistics will be presented:

Table 5.1: Descriptive statistics produced

Baseline characteristics and follow-up description	Categorical data	Number of subjects. Percentage of subjects.
	Continuous data	Mean, standard deviation, quartiles, minimum, and maximum.
Clinical safety results	Categorical data	Solicited: Number and percentage (95% CIs) of subjects. Unsolicited: Number and percentage (95% CIs) of subjects, and number of events.
	Continuous data	Mean, standard deviation, quartiles, minimum, and maximum.
Immunogenicity results	Categorical data (seroconversion, 2 fold-rise, 4 fold-rise)	Number and percentage (95% CIs) of subjects.
	Continuous data (titer / data[†])	Log10: Mean and standard deviation. Anti-Log10 (work on Log10 distribution, and anti-Log10 applied): Geometric mean, 95% CI of the geometric mean, quartiles, minimum, and maximum. Graphical representation by Reverse Cumulative Distribution Curve (RCDC).
Efficacy results	Categorical data	Number and percentage (95% CIs) of subjects.

The CI for the single proportion will be calculated using the exact binomial method (Clopper-Pearson method, quoted by Newcombe (5), i.e., using the inverse of the beta integral with SAS®).

For immunogenicity results, assuming that Log10 transformation of the titers / data follows a normal distribution, at first, the mean and the 95% CI will be calculated on Log10 (titers / data) using the usual calculation for normal distribution (using Student's t distribution with n-1 degree of freedom), then antilog transformations will be applied to the results of calculations, in order to provide geometric means (GMs) and their 95% CI.

5.1 Statistical Methods

Safety, immunogenicity, and efficacy analyses will be undertaken including those data collected before the date of receiving an authorized/approved COVID-19 vaccine. Those data collected on or after receiving an authorized/approved COVID-19 vaccine will be listed separately.

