In addition to antibody response 21 days after the first injection, durability after a single injection also needs to be taken into account for schedule selection decisions, as peak immune responses after 1 injection may be adequate but could (at least theoretically) wane rapidly, potentially leaving vaccinees at risk in the event of ongoing circulation of the novel coronavirus. A further consideration is allowing sufficient time for contraction of innate immune responses and expansion of the adaptive immune response after dosing, which would be underestimated if evaluated too soon after the dose. In this regard, at least fourteen days after a second dose is deemed sufficient, based on experience with other vaccines (27) (31) (32). Therefore, antibody titers at D22 (21 days after the first injection) and D36 (14 days after a second injection) after a single injection or after 2 injections are considered relevant for informing schedule selection.

Rationale for Primary Immunogenicity Endpoint

Human experimental coronavirus infection studies have identified that the presence of pre-challenge neutralizing antibodies were predictive of protection from infection or symptoms following challenge (33) (34). For this reason, neutralizing responses are expected to provide the most relevant functional evaluation of immune responses for this vaccine candidate.

Rationale for Study Population

The study will enroll participants with no history of COVID-19 or serologic evidence of SARS-CoV-2 infection by rapid diagnostic test at the baseline visit. Inclusion of individuals with prior exposure to SARS-CoV-2 would be expected to influence immunogenicity measures. This trial is geared to identifying the dose-level of CoV2 preS dTM vaccine formulation that best supports an immune response in the naïve population, considered the population most at need for a preventive solution against SARS-CoV-2. Therefore, the immunogenicity and safety data in this study are targeted to be generated in individuals without evidence of prior exposure to SARS-CoV-2 infection.

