9.3 Populations for Analyses

The following populations are defined:

Population	Description
Randomized	All participants with a randomized group that has been allocated by IRT
Safety Analysis Set (SafAS)	Subset of randomized participants who have received at least one injection of study intervention. Participants will have their safety analyzed according to the study intervention they actually received. Safety data recorded for a vaccine received out of the protocol design will be excluded from the analysis (and listed separately).
Full analysis set (FAS)	Subset of randomized participants who received at least 1 injection of the study intervention. Participants will be analyzed according to the study intervention group to which they were randomized.
Per-protocol analysis set (PPAS)	Subset of the FAS. Participants presenting with at least one of the following relevant conditions will be excluded from the PPAS: 
 • Participant did not meet all protocol-specified inclusion criteria or met at least one of the protocol-specified exclusion criteria • Participant did not complete the protocol-defined vaccination schedule • Participant received a study intervention other than the one that he / she was randomized to receive • Preparation and / or administration of study intervention was not done as per-protocol • Participant did not receive study intervention in the proper time window • Participant received a Category 2 or Category 3 therapy / medication / as stated in Section 6.5 • Participant with positive test results in the ELISA and/or neutralization test at baseline • Additional conditions for exclusion may be identified during the review of protocol deviations; such conditions will be documented in the Statistical Analysis Plan (SAP)
Per-protocol analysis set for immunogenicity (PPAS-IAS)	Subset of PPAS excluding participants who provided all post-dose serology samples outside the proper time window or no post-dose serology sample was drawn.
Per-protocol analysis set for CMI (PPAS-CMI)	Subset of PPAS excluding participants who provided all post-dose CMI samples outside the proper time window or no post-dose CMI sample was drawn.

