4.4.2.3 Seroconversion

The seroconversion endpoint is driven by both baseline and post-baseline computed values (assuming replicate values have been reduced to one value as described in Section 4.4.2.1) and a subject will have seroconverted if baseline values below LLOQ with detectable neutralization titer above assay LLOQ at D22, D36, D181 (Cohort 1) or D202 (Cohort 2), and at D366 (Cohort 1) or D387 (Cohort 2).

Note: If baseline or post-baseline is missing, then seroconversion is missing.

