5.1.2.2 Statistical Methods for Secondary Immunogenicity Objectives

For descriptive purposes, the statistics presented on [Table 5.1](#) will be produced.

Immunogenicity analyses will be performed in those BL collected before receiving an authorized/approved COVID-19 vaccine. Immunogenicity data after receiving an authorized/approved COVID-19 vaccine will be listed separately.

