5.2.3 Per-Protocol Analysis Set

Subset of the FAS. Participants presenting with at least one of the following conditions will be excluded from the PPAS:

- Participant did not meet all protocol-specified inclusion criteria or met at least one of the protocol-specified exclusion criteria
- Participant did not complete the protocol-defined vaccination schedule
- Participant received a study intervention other than the one that he / she was randomized to receive
- Preparation and / or administration of study intervention was not done as per-protocol
- Participant did not receive study intervention in the proper time window as defined in the protocol visits.
- Participant received a Category 2 or Category 3 therapy /medication / as stated in Section 6.5 of the Protocol
- Participant with positive test results in the neutralization test at baseline.

The above conditions leading to exclusion from the PPAS may be detailed and completed if necessary following the data review. In any case, if PPAS definition is modified, the PPAS definition will be finalized before the database lock and documented in an SAP update.

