5.2.3.1 Per-Protocol Analysis Set for immunogenicity (PPAS-IAS)

Subset of PPAS excluding participants who provided all post-dose serology samples outside the proper time window or no post-dose serology sample was drawn

For participants with just part of expected post-dose serology samples outside the proper time window or without a valid test result, participants will be kept in PPAS-IAS and only samples within the time window and with a valid result will be included in immunogenicity analyses.

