5.2.5 Populations Used in Analyses

The primary immunogenicity analyses, the secondary immunogenicity analyses, and the exploratory immunogenicity analyses (excluding CMI analyses) will be performed on the PPAS-IAS, and will be confirmed on the FAS.

The primary safety analysis will be performed on the SafAS.

The secondary efficacy analyses will be performed on FAS and PPAS-IAS.

The CMI analyses in the exploratory objective will be performed on PPAS-CMI, and will be confirmed on the FAS.

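### Samples drawn after an in-trial SARS-CoV-2 infection stay in the per-protocol immunogenicity summaries, so the 6- and 12-month results mix infection antibody with persistence

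*SAP*

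**What the plan says.** Four rules decide which antibody results are summarised.

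- **Cut-off date.** SAP 5.1 states: "Safety, immunogenicity, and efficacy analyses will be undertaken including those data collected before the date of receiving an authorized/approved COVID-19 vaccine". SAP 5.1.2.2 repeats it for the secondary objectives: "Immunogenicity analyses will be performed in those BL collected before receiving an authorized/approved COVID-19 vaccine". An outside vaccine is the only event after baseline that ends a participant's contribution.
- **Per-protocol exclusions.** The item closest to infection in SAP 5.2.3 is "Participant with positive test results in the neutralization test at baseline". Protocol 9.3 has "Participant with positive test results in the ELISA and/or neutralization test at baseline". Both concern baseline only.
- **Sample-level rule.** Within the PPAS-IAS (SAP 5.2.3.1), "only samples within the time window and with a valid result will be included in immunogenicity analyses".
- **Endpoint definition.** SAP 4.4.2.3 says "a subject will have seroconverted if baseline values below LLOQ with detectable neutralization titer above assay LLOQ at D22, D36" and at the later visits. It sets no condition on infection status, and neither does fold-rise in SAP 4.4.2.2.

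Infection enters the antibody summaries at one point. SAP 5.1.3 adds an exploratory description of the final pre-infection titre and concentration, pooled into all vaccine and all placebo. SAP 5.2.5 says that the immunogenicity analyses ("excluding CMI analyses) will be performed on the PPAS-IAS, and will be confirmed on the FAS"), but the FAS has no infection rule either.

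**The concern.** The plan removes baseline positives and samples after an outside vaccine, both of which carry antibody that the study injection did not produce. Infection during follow-up does the same, and its samples stay in. A participant infected around D100 contributes post-infection titres at D181/D202 and D366/D387 as if they showed how long the vaccine response lasts.

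The Protocol accepts the premise. Its population rationale in 4.2 says: "Inclusion of individuals with prior exposure to SARS-CoV-2 would be expected to influence immunogenicity measures".

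At stake are the secondary persistence results by arm. Antibody acquired by infection can mask waning in the vaccine arms and produce responders in the placebo arms. It can also move the between-group GMT ratios and seroconversion differences planned in Protocol 9.4.2.1 and 9.4.3.1.

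**Working it through.** **Plan's own figure.** There is none on this point: no attack rate, no post-infection titre rise, no power calculation. The arm sizes in Protocol Table 4.2 do add up: 300 younger (5×20, then 4×20 + 2×60) plus 140 older (5×10, then 3×10 + 2×30) = 440.

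**Can infection be identified from planned data?** Yes.
- Protocol Table 8.1 has anti-N ELISA at all six serum time points, including D113/D134, when neutralization and anti-S are not run.
- Respiratory samples for NAAT are taken at illness visits throughout the study (Protocol 8.2.2.2).
- Protocol 9.4.3.2 already defines serological infection as conversion from negative to positive in the non-spike assay.
- The vaccine antigen is spike only (Protocol 2.2), so anti-N conversion points to infection.

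**Effect on a GMT.** The log10 GMT is the mean of the log10 titres. If a share f of an arm has its titre multiplied by F, the mean rises by f × log10(F), so the GMT is multiplied by F^f. The geometric mean fold-rise changes by the same factor. Both f and F are assumptions.

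| Share infected f | F = 10 | F = 100 |
|---|---|---|
| 1% | 1.02 | 1.05 |
| 3% | 1.07 | 1.15 |
| 5% (1 of 20) | 1.12 | 1.26 |
| 10% (1 of 10, or 3 of 30) | 1.26 | 1.58 |
| 15% | 1.41 | 2.00 |

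Taking 1–3% as an assumption for D36 gives 1.02 to 1.15. Taking 5–15% for the late visits gives 1.12 to 2.00. In an arm of 60, one infection gives 10^(1/60) = 1.04 to 100^(1/60) = 1.08.

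**Chance that an arm is affected.** P(at least one infected) = 1 − (1 − f)^n. For n = 20 this is 18%, 46%, 64% and 88% at f = 1%, 3%, 5% and 10%. For n = 30 it is 26%, 60%, 79% and 96%.

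**Effect on seroconversion.** Take 30 placebo recipients with no other responders. With no infections the table shows 0/30 (Clopper-Pearson 95% CI 0 to 11.6%). With three infections, all above LLOQ at the visit, it shows 3/30 = 10% (2.1 to 26.5%).

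**Effect on the vaccine/placebo GMT ratio.** With f = 10% in both groups, but F = 10 in vaccine and 30 in placebo, the ratio is multiplied by 10^0.10 / 30^0.10 = 0.90. With f = 5% and F = 10 in vaccine, against f = 10% and F = 30 in placebo, it is multiplied by 10^0.05 / 30^0.10 = 0.80. Other inputs could reverse the direction.

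**After the change.** For infections that are detected, the multiplier returns to 1.00 and the placebo example to no responders.

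**The case against.** The strongest case against has five parts.

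1. **Few cases are likely to reach the analysis.** SAP 5.1.2.4 expects a limited number of COVID-19 cases before outside vaccination, and the existing cut removes all samples after such a vaccine. One cannot assume both a full year of exposure and many retained late samples. This stands, and it limits the size.
2. **The shift is small beside sampling error.** For n = 20 and an assumed log10 SD of 0.3 to 0.6, the 95% CI half-width is a factor of 10^(2.093 × SD/√20) = 1.38 to 1.91, against 1.12 to 1.26 from one infection. This stands as a limit on interpretation. A wide interval still does not show a reader that the point estimate is shifted.
3. **The plan has partial safeguards.** The pre-infection summary in SAP 5.1.3 is pooled and does not correct the results by arm. Both documents allow PPAS exclusions to be added before lock, but neither names infection. Category 2 or 3 medication removes some infected participants, but reportable medication is collected only in the post-vaccination windows (Protocol 6.5), and mild or asymptomatic infection escapes.
4. **Keeping everyone is a legitimate as-observed description.** It is, and the FAS is the place for it. At present both sets give that description and neither gives the other.
5. **Censoring has its own bias.** Infection occurs after randomisation and may depend on titre. If low responders are infected more often, removing their later samples leaves higher responders and can also hide waning. This stands and shapes the fix.

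A reader might also take the sentence from Protocol 4.2 as a rule that is being broken. It justifies enrolling a naive population and sets no rule for infection after randomisation. It supports the reasoning only.

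**Conclusion.** The gap is real, in both documents, and concerns chiefly the per-protocol results at D181/D202 and D366/D387. In vaccine arms those results mix infection antibody with persistence. In placebo arms they show apparent response.

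The size cannot be fixed from the documents. The figure of 1.12 to 1.26 for one infection in an arm of 20 rests on an assumed 10- to 100-fold rise over the titre otherwise present. That may be generous in vaccinees who have already responded.

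Three stronger readings are not supported:

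- **That formulation selection is compromised.** Selection uses immunogenicity to D36 and safety to D43 (Protocol 4.2 and 9.5), where the illustrated effect is small. All analyses are descriptive, so no test or decision rule is affected.
- **That infection makes the vaccine look better.** In placebo arms the antibody appears as placebo response. If infection is more frequent there, the contrast with vaccine shrinks.
- **That placebo seroconversion at 12 months would equal the attack rate.** That is an upper bound. It needs every infected placebo recipient to remain above LLOQ and not to have been cut for an outside vaccine.

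The point is worth correcting because persistence is a stated secondary objective and the data needed are already collected. It does not threaten the trial's main conclusions.

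**What to change.** In SAP 5.1 and 5.2.3.1, add a rule for the PPAS-IAS immunogenicity summaries: leave out any sample drawn on or after the first NAAT-positive illness or the first serum sample showing anti-N conversion from negative to positive, whichever is earlier. The conversion sample itself is left out. State which date marks the illness, and use the conversion definition in Protocol 9.4.3.2.

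List the excluded samples by arm. Keep post-infection samples, up to any outside vaccine, in the FAS summary already planned in SAP 5.2.5, and present the two results together.

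The cost is one sentence, one derived flag and a few late samples lost from the per-protocol tables. There is also the possible selection if low responders are infected more often. That is why the uncensored FAS result must be reported beside the censored one. The rule catches only infections that NAAT or anti-N detects.

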5.1.1 Hypotheses and Statistical Methods for Primary Objectives

5.1.1.1 Primary Safety Hypotheses

No hypotheses will be tested.

5.1.1.2 Statistical Methods for Primary Safety Objective

Safety results will be described for each age and vaccine group. The homogeneity of pooled groups will be assessed on the main parameters. The main parameters will be described with 95% CI.

Safety analyses will be performed based on safety analysis set including safety data collected before the date of receiving an authorized/approved COVID-19 vaccine. Safety data collected on or after the day of receiving an authorized/approved COVID-19 vaccine will be listed separately.

Solicited Reactions

Number and percentage of subjects with:

- Presence of solicited injection site reactions and systemic reactions occurring up to 7 days after injection
- Each solicited reaction according to time of onset, maximum intensity, and number of days of occurrence over the solicited period

Unsolicited Events and Reactions

Number and percentage of subjects with:

- Any unsolicited immediate systemic event in the 30 minutes after injection
- Any unsolicited event and reaction (using the current MedDRA version) 21 days after injection
- Any unsolicited event/reaction according to time of onset, maximum intensity, and duration

SAEs

Number and percentage of subjects with:

- any SAE within 21 days after injection and during the 6 months and 12 months follow-up periods according to SOC and PT, seriousness and outcome

AEs of special interest

- Number and percentage of subjects with any/each AESI within 21 days after injection and during the 6 month and 12 months follow-up periods will be presented according to SOC and PT, seriousness and outcome.

MAAE

- Presence of medically attended adverse events (MAAEs) throughout the study

Laboratory tests

- Presence of out-of-range biological test results up to 7 days post-last dose (ie, up to D09 for Cohort 1 and up to D30 for Cohort 2)

The following analyses will be performed for laboratory tests in addition to the summary of out of range tests above:

- Biological test results and toxicity grade by visit,

- Summary of toxicity grade shift from baseline,

For descriptive purposes, the statistics presented on [Table 5.1](#) will be produced.

In addition to analyses by each intervention group, aggregated groups will be used to perform complementary assessments for above parameters, including:

1. aggregated vaccine group, ie, all vaccine arms pooled
2. aggregated placebo group, ie, two placebo arms pooled
3. aggregated dose-level group, ie, low-dose arms pooled, or high-dose arms pooled
4. aggregated adjuvant type group, ie, AF03 arms pooled or AS03 arms pooled

The analyses by aggregated groups will also be conducted in overall population and by age group.

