4.4.1.2.6 Serious Adverse Event (SAE)

SAEs will be analyzed throughout the study using the following periods:

- During post-Dose 1 period (i.e., between injection 1 and injection 2), and during 21 days after the last injection
- During the 6-month follow-up period
- During the 12-month follow-up period

- During the study (i.e., all SAEs occurred during the study)

Additionally, a table will present all SAEs during the study in order to count all SAE collected.

Note: SAE that occurred before vaccination (negative time of onset) will not be included in analysis, but will be listed separately.

Safety analysis will include only those SAEs with time of onset before a participant received a non-study authorized/approved COVID-19 vaccine, if applicable. SAEs with time of onset on or after the date of receiving a non-study authorized/approved COVID-19 vaccine will be listed separately.

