4.4.1.4.7 AESI

AESIs (serious and non-serious) will be collected throughout the study to ensure that events are communicated to the Sponsor in an expedited manner and followed-up until the end of the follow-up period or resolution, as per the assigned causality.

Anaphylactic reactions, generalized convulsions, thrombocytopenia, dry eyes, tearing, dry mouth, NOCMCs and pIMDs.

NOCMCs

NOCMCs are defined as any new ICD-10 diagnosis (10th revision of the International Statistical Classification of Diseases and Related Health Problems) that is applied to the participant during the course of the study, after receipt of the study agent, that is expected to continue for at least 3 months and requires continued health care intervention.

pIMDs

Potential immune-mediated diseases (pIMDs) are a subset of AEs that include autoimmune diseases and other inflammatory and/or neurologic disorders of interest which may or may not have an autoimmune etiology. AEs that need to be recorded and reported as pIMDs include those listed in Table 10.5 of the protocol.

AESIs will be analyzed throughout the study using the following periods:

- During post-Dose 1 period (i.e., between injection 1 and injection 2), and during 21 days after the last injection
- During the 6-month follow-up period
- During the 12-month follow-up period
- During the study (i.e., all AESIs occurred during the study)

Safety analysis will include only those AESIs with time of onset before a participant received a non-study authorized/approved COVID-19 vaccine, if applicable. AESIs with time of onset on or after the date of receiving a non-study authorized/approved COVID-19 vaccine will be listed separately.

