4.4.1.4.8 Medically Attended AE (MAAE)

An MAAE is a new onset or a worsening of a condition that prompts the participant to seek unplanned medical advice at a physician's office or Emergency Department. Physician contact made over the phone or by e-mail will be considered a physician office visit for the purpose of MAAE collection. This includes medical advice seeking during the study visit or routine medical care. This definition excludes pediatric check-ups, follow-up visits of chronic conditions with an onset prior to entry in the study, and solicited reactions.

MAAE will be analyzed during the following time periods:

- During post-Dose 1 period (i.e., between injection 1 and injection 2), and during 21 days after the last injection
- During the 6-month follow-up period
- During the 12-month follow-up period
- During the study (i.e., all MAAEs occurred during the study)

Safety analysis will include only those MAAEs with time of onset before a participant received a non-study authorized/approved COVID-19 vaccine, if applicable. MAAEs with time of onset on

or after the date of receiving a non-study authorized/approved COVID-19 vaccine will be listed separately.

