5.2.2 Safety Analysis Set

Subset of randomized participants who have received at least one injection of study intervention. Participants will have their safety analyzed according to the study intervention they actually received. All subjects will be analyzed after each dose according to the vaccine they actually received, and after any dose according to the vaccine received at the 1st dose.

Safety data recorded for a vaccine received out of the protocol design will be excluded from the analysis (and listed separately).

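### The 6-month, 12-month and whole-study SAE, AESI and MAAE percentages stop counting events at an outside COVID-19 vaccine but make no allowance for the shortened follow-up, so they are too low if read as risk over the period

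*SAP*

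**What the plan says.** **Periods.** For SAEs, SAP 5.1.1.2 summarises "any SAE within 21 days after injection and during the 6 months and 12 months follow-up periods". It gives AESIs the same periods. For MAAEs that section speaks only of the study as a whole; the separate periods, including "During the 12-month follow-up period", are in SAP 4.4.1.4.8. SAP 4.4.1.2.6, 4.4.1.4.7 and 4.4.1.4.8 each add a whole-study period.

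**Which events count.** For SAEs: "Safety analysis will include only those SAEs with time of onset before a participant received a non-study authorized/approved COVID-19 vaccine". SAP 4.4.1.4.7 ("Safety analysis will include only those AESIs with time of onset before a participant received a non-study authorized/approved COVID-19 vaccine") and 4.4.1.4.8 ("Safety analysis will include only those MAAEs with time of onset before a participant received a non-study authorized/approved COVID-19 vaccine") repeat the rule. Events from the day of the outside vaccine onward go to separate listings.

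**Who is analysed.** SAP 5.1.1.2: "Safety analyses will be performed based on safety analysis set including safety data collected before the date of receiving an authorized/approved COVID-19 vaccine". SAP 5.2.2 defines that set: "Subset of randomized participants who have received at least one injection of study intervention". Nothing there removes or censors a participant after an outside vaccine.

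**Statistic.** SAP Table 5.1: "Unsolicited: Number and percentage (95% CIs) of subjects, and number of events". The intervals are Clopper-Pearson. Neither document plans person-time, exposure-adjusted rates or Kaplan-Meier estimates for these tables.

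**Objective.** The primary safety objective (Protocol Table 3.1, SAP 2.1) is to describe safety in each age and intervention group up to 12 months after the last dose.

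**The concern.** A participant who takes an authorised vaccine in month 4 can contribute no SAE, AESI or MAAE to the tables afterwards. Under the SafAS definition that participant still counts in the 12-month percentage, and counts as event-free. The percentage then describes events seen before an outside vaccine, while its period label invites a reader to take it as 12-month risk, which is what the primary safety objective is about.

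The SAP deals with the same truncation over short windows. It treats the outside-vaccine date as a censoring date for days of occurrence (4.4.1.1.5). It sets overall days, ongoing status, and the intensity and duration of straddling AEs to missing (4.4.1.1.6, 4.4.1.1.7, 4.4.1.2.2, 4.4.1.2.5). It limits the solicited-reaction denominator to evaluable participants (4.4.1.1.3). The long periods, where most follow-up can be lost, have no counterpart. Truncation is also expected: SAP 5.7 records the amendment allowing outside vaccination and foresees few COVID-19 cases before it.

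**Working it through.** **The plan's own figures.** The documents state no long-term event rate and no uptake. The arm sizes do add up: 300 + 140 = 440, the largest possible SafAS. The pooled safety groups are 380 vaccine and 60 placebo.

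**Assumptions.** R is the true 12-month risk, u the share taking an outside vaccine, and x the day it is taken, counted from the last injection. The windows are 180 and 365 days, from the visit schedule. Uptake is taken as unrelated to event risk.

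**Step 1: retained follow-up.** The share of person-time kept over 365 days is 1 − u(1 − x/365). With u = 0.5 and mean x = 180 it is 1 − 0.5 × (1 − 0.493) = 0.747. A true 4% then shows as about 0.747 × 4% = 3.0%.

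**Step 2: constant-hazard check.** With h = −ln(1 − R)/365, the planned percentage over T days is

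(1 − u)(1 − e^(−hT)) + u(1 − e^(−h·min(x, T))).

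For R = 4%, u = 0.5 and x = 180: 0.5 × 4.00% + 0.5 × 1.99% = 3.0%, as in step 1.

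**Step 3: range, for R = 10% over 12 months.**

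| Uptake | Vaccine on day 90 | Day 150 | Day 240 |
|---|---|---|---|
| 20% | 8.5% | 8.9% | 9.3% |
| 50% | 6.3% | 7.1% | 8.3% |
| 80% | 4.1% | 5.4% | 7.4% |

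Over R from 3% to 30% and the same grid, the relative understatement runs from 6% to 60%.

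**Step 4: the 6-month window, R = 10%.** For uptake of 20%, 50% and 80%, the percentage is 10%, 25% and 39% too low in relative terms with vaccination at day 90, and 3%, 8% and 13% too low at day 150. It loses nothing if vaccination falls after day 180.

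**Step 5: unevenness.** Take two groups with the same true 10% risk and vaccination at day 120.

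- Uptake 30% against 80% gives 8.0% against 4.7%, a spurious ratio of 0.59.
- Uptake 50% in both gives 6.7% in both, ratio 1.00.

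So unevenness needs a difference in uptake or timing. A smaller route is the schedule: an outside vaccine on study day 150 leaves 149/365 = 41% of the 12-month window in Cohort 1 and 128/365 = 35% in Cohort 2.

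**Step 6: the rate.** Under the same model, events over person-time recover the risk by construction. For R = 10% and vaccination at day 120:

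- 30% uptake: 0.0802 events over 0.761 person-years per participant = 10.5 per 100 person-years.
- 80% uptake: 0.0472 over 0.448 = 10.5 per 100 person-years.

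Both convert back to a 365-day risk of 10.0%.

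**The case against.** **The denominator is inferred.** No sentence gives it for these tables. It follows from the SafAS definition, and the SAP sets special denominators elsewhere. This stands, and is why stating the denominator comes first in the fix.

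**The cut-off is deliberate and disclosed.** Both documents say that data up to the outside vaccine are used. As a description of events before an outside vaccine, the percentage is correct. This also stands; the fault lies in reading it as risk over the named period.

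**A reader might infer that the arms are distorted unevenly.** The documents do not show this. Arms are randomised within age strata and observer-blind (Protocol 6.3.1, 6.3.2), and unblinding is not required before an outside vaccine (Protocol 7.1.2), so similar uptake across arms within a stratum and cohort is the natural expectation. The age mix is nearly the same in pooled vaccine (260 younger, 120 older) and pooled placebo (40 and 20). The Cohort 2 share differs (260/380 = 68% against 30/60 = 50%), but the effect of that is small. Differences remain possible by age through eligibility (SAP 5.7), or after the interim results are published (SAP 5.4).

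**A reader might infer that the truncation is informative.** Nothing shows that outside vaccination depends on event risk. The understatement does not need it, and an exposure-adjusted rate would not cure it.

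**Later events are not lost.** They are listed, and SAP 4.4.1.2.6 plans a table of all SAEs collected. The same section restricts the safety analysis to onsets before an outside vaccine, so that table's scope is unclear. Listings do not correct a percentage.

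**Precision is low.** Age-by-arm cells hold 10 to 60 people, and 0/10 has an interval of 0 to 30.8%. Even among 380 pooled vaccinees, 15 events (3.9%; 2.2 to 6.4%) and 11 events (2.9%; 1.5 to 5.1%) overlap widely. Formulation selection rests on data to D43 (Protocol 4.2). This limits the consequences, but describing 12-month safety is itself the primary objective.

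**Conclusion.** The concern holds in a limited form. Events stop at the outside vaccine, the analysis set does not shrink, and no time-at-risk summary is planned. Read as risk, the 12-month percentages are too low whenever outside vaccination falls within 12 months of the last injection. The 6-month ones are too low only when it falls within that shorter window. Unevenness is conditional on differing uptake or timing.

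Every size rests on assumed uptake, timing and risk, because the documents give none. The example of 4% shown as 3.0% is illustrative. Recovery of the true risk by the rate also needs a constant hazard and outside vaccination unrelated to event risk.

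**What to change.** 1. State in SAP 5.1.1.2 that the n (%) denominator for the 6-month, 12-month and whole-study SAE, AESI and MAAE tables is the full SafAS, and label the percentage as events observed before an outside COVID-19 vaccine.
2. Report vaccine-free person-time by arm and age group.
3. Beside n (%), add participants with an event per 100 person-years to the first of event, outside vaccine or end of follow-up, with exact Poisson intervals.
4. Because the rate assumes a constant hazard and vaccination unrelated to risk, also tabulate all events regardless of outside vaccination as a sensitivity summary.
5. Reconcile Protocol 6.5, which names only influenza vaccination as collected throughout, with the schedules of activities (Protocol Tables 1.1 and 1.2, SAP Tables 3.1 and 3.2), which record influenza and COVID-19 vaccinations in later follow-up. The censoring date depends on it.

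The cost is a few table columns and one extra summary. The SAP's existing cut-off rules already need the outside-vaccine date, so no new data item is required once the collection text is consistent.
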